4.2.1.3 Handling of Dropouts and Missing Data

No data imputation for the primary endpoint.

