At the IPD Visit the participants will be given the following 3 options as to how they will be followed:

- 1. The participant should be encouraged to return for all regular clinic visits and perform all scheduled assessments (excluding IP administration) until the EOT visit at Week 52 (± 5 days).
- 2. The participant will be offered follow-up on a monthly basis via telephone calls while continuing ePRO data collection on the handheld device at home (no further procedure will be performed) until the participant completes the on-site EOT visit at Week 52 (± 5 days).
- 3. If the participant cannot or does not wish to comply with any of the options above (or any component of them such as only telephone-based visits without completion of the ePRO data), the investigator will contact the participant via telephone at 52 weeks after baseline. No other study assessments will be performed prior to this contact.

Participants who discontinue IP with option 1 or 2 are allowed to further reduce their OCS dose following the same protocol-specified OCS dose reductions scheme as participants being still on-treatment.

If the last study intervention administration was after Week 36 for options 1 or 2, the participant will return to the clinic for an EOT visit at Week 52 (\pm 5 days). For option 3, the investigator will contact the participant at 52 weeks post baseline.

If a participant chooses option 1, all assessments will be completed as per the SoA as indicated in Table 1. If a participant chooses option 2 or 3, the key information to be collected during the telephone calls are AESIs/DAEs/SAEs, changes in concomitant medication, and asthma exacerbation information.

Participants who initially choose options 1 or 2 and subsequently cannot or do not wish to comply with the requirements of their option can continue with a less intensive option

(ie, participants initially choosing option 1 can continue with options 2 or 3, participants initially choosing option 2 can continue with option 3).

If a participant discontinues tezepelumab due to a study specific discontinuation criterion, this should always be recorded as 'Development of study specific discontinuation criteria' on the Discontinuation of IP form in the eCRF.

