9.4.3 Efficacy

9.4.3.1 Primary Endpoints

The following outcomes are designed to support the primary objective of the study:

- Proportion of participants who discontinue OCS without loss of asthma control
- Proportion of participants who reduce OCS dose to ≤ 5 mg/day without loss of asthma control

The baseline OCS dose is defined in Section 9.4.1. The final OCS dose is defined based on the prescribed maintenance dose, expressed as a dose per day, at Week 28 or Week 52. If the participant is on a fixed daily dose, then the OCS dose is defined as that prescribed dose. If the participant is on every other day regimen, then the OCS dose is defined as the average amount prescribed to be taken each day. Final daily OCS dose will be derived as described in Table 13. Further details may be specified in the SAP.

Table 13 Final Daily Maintenance OCS Derivation

Situation	Final daily maintenance OCS dose
Initiation of therapy with another biologic for treatment of asthma	Last reported OCS dose ^a received by participant with asthma stability verified ^b prior to initiation of another biologic.
Premature withdrawal from the study	Last reported OCS dose ^a received by participant with asthma stability verified ^b at the time of study withdrawal.
Any other situation	Last reported OCS dose ^a received by participant with asthma stability verified ^b

^a daily OCS dose is based on information collected in ECSYSCRT eCRF.

Each primary endpoint will be summarised by number and proportion (with 95% CI) of participants. The 95% CIs for proportions will be calculated using the Clopper-Pearson exact method.

Analysis of the primary endpoints will be based on both the FAS population and the current or historical elevated EOS population. In addition, primary endpoints will be summarised by pre-specified subgroups using FAS population including (but not limited to):

- Baseline EOS group: $< 300/\mu L$, $\ge 300/\mu L$
- Baseline EOS group: $< 150/\mu L, \ge 150/\mu L$.

Any further requirements for subgroups analysis and exact definition of all relevant categories where needed, will be pre-specified in the SAP.

^b Asthma stability is defined as no change in OCS dose for at least 2 weeks.

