3.3 General Considerations

In general, continuous endpoints are summarised using the mean, the standard deviation, median, minimum value, and maximum value, and the categorical endpoints are summarised using frequency counts and percentages, as well as a two-sided 95% CI for proportions computed using exact Clopper-Pearson method. Time to event data is presented graphically using Kaplan Meyer curve.

Absolute change from baseline is defined as (post-baseline value – baseline value). The percent change from baseline is defined as {(post-baseline value – baseline value)/baseline value)}*100. Baseline calculations are defined in the Section 3.3.1.2.

For participants' proportion calculation, the denominator is the number of participants in the Full Analysis Set defined in Section 4.1.2 unless otherwise stated.

No imputation performed beyond the approach defined for outcome measures. Imputation for partial date is detailed in the Appendix A.

Unless specified otherwise, the daily maintenance OCS dose, including the daily OCS at baseline (Section 3.3.1.2) and the final daily OCS dose (Section 4.2.1.2), is defined based on the prescribed maintenance dose of OCS, expressed as a dose per day, at the time of the relevant visit. If a participant is on a fixed daily dose, then the OCS dose is defined as that prescribed dose. If the participant is on every other day regimen (or different doses every other day), then the OCS dose is defined as the average amount prescribed to be taken each day. For example, should a participant be on a 10 mg every other day regimen of OCS, their OCS dose is defined as 5 mg.

Maintenance dose of OCS is collected on the ECSYSCRT eCRF page with a therapy reason of "Asthma maintenance dose", "Titration, due to asthma", "AI based on cortisol test", "Signs/symptoms of AI" and "Adrenal crisis". If the maintenance OCS doses with more than one therapy reasons (including only those mentioned earlier) are prescribed on the same day (e.g., "Asthma maintenance dose" and in addition "Signs/symptoms of AI"), then the sum of the doses are calculated.

Note that the prescribed OCS dose with therapy reason of "Asthma exacerbation per protocol" or "Worsening of asthma, without exacerbation" is not included in the daily OCS dose calculation. In case of overlapping OCS doses taken for asthma worsening or exacerbation with maintenance doses of OCS, the latter one is excluded from the daily OCS dose calculation.

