4.2.1.1 Definition

The following primary endpoints are designed to support the primary objective of the study:

- Proportion of participants who discontinue OCS without loss of asthma control
- Proportion of participants who reduce OCS dose to ≤ 5 mg/day without loss of asthma control

Both proportions are assessed at Week 28 and at Week 52.

4.2.1.2 **Derivations**

The baseline OCS is defined in Section 3.3.1.2. The final OCS dose at Week 28 (Visit 9) or at Week 52 (Visit 15) is defined as in Section 3.3 and Table 4. Strategies of handling intercurrent events are presented in Section 4.2.

Table 4 Final daily maintenance OCS derivation

Situation	Final daily maintenance OCS dose
Initiation of therapy with another biologic for treatment of asthma	Last reported OCS dose ^a received by participant with asthma stability verified ^b prior to initiation of another biologic for treatment of asthma.
Premature withdrawal from the study	Last reported OCS dose ^a received by participant with asthma stability verified ^b at the time of study withdrawal.
Any other situation	Last reported OCS dose ^a received by participant with asthma stability verified ^b

^a daily OCS dose is based on information collected in ECSYSCRT eCRF.

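### The primary endpoint carries the last stable OCS dose forward for participants who leave the study, and no planned analysis shows how many successes depend on it

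*SAP*

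**What the plan says.** SAP 4.2.1.3, the section on dropouts and missing data for the primary endpoint, consists of one statement: "No data imputation for the primary endpoint". SAP 3.3 is less absolute: "No imputation performed beyond the approach defined for outcome measures".

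Table 4 in SAP 4.2.1.2, which matches protocol Table 13, derives the final daily dose in three rows:

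- Start of another asthma biologic: the last stable dose before that start.
- "Premature withdrawal from the study": the last stable dose "at the time of study withdrawal".
- "Any other situation": the last stable dose.

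Stable means that the dose did not change for at least two weeks. For proportions, SAP 3.3 says that "the denominator is the number of participants in the Full Analysis Set".

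The estimand tables (protocol Section 3, SAP 1.1) list three intercurrent events. Treatment discontinuation and change in background therapy follow treatment policy; start of another asthma biologic follows the hypothetical strategy. Withdrawal from the study is not listed.

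SAP 4.2 and 4.2.1.5 plan no sensitivity analysis. SAP 4.2.1.6 plans one on-treatment supplementary analysis. Protocol 9.4.3.1 leaves room for more: "Further details may be specified in the SAP".

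**The concern.** The trial has one arm and tests no hypothesis, so the proportion and its interval are the result. For a participant who has left, Table 4 assumes that the last stable dose would have lasted to Week 28 or Week 52. The Clopper-Pearson interval treats that status as observed.

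A concrete case: protocol 5.1 admits participants on 5 mg/day. Someone who enters at 5 mg, stays stable and withdraws early meets the dose part of the ≤ 5 mg endpoint at both Week 28 and Week 52, with no later dose seen. The Week 28 versus Week 52 shift table in SAP 4.2.1.4 would show that one dose at both times, as if it had been maintained.

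A reader of the report could not separate successes supported by a dose record at the visit from successes that rest on this assumption.

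**Working it through.** **1. What kind of rule this is.** For starters of another biologic, carrying the dose forward is the declared hypothetical strategy. For study withdrawals no strategy is declared, yet each one counts in the denominator and needs a status. Assigning the last stable dose is therefore missing-data handling by single imputation. SAP 4.2.1.3 neither names it nor refers to Table 4.

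**2. Who else may lack a dose record.** Under follow-up option 3 (protocol 7.1) the participant stops tezepelumab and is telephoned at 52 weeks: "No other study assessments will be performed prior to this contact". The call does collect medication changes, so it may recover the Week 28 dose. At the primary database lock it may not yet have taken place.

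**3. What the planned outputs would show.**

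| Output | Shows withdrawn participants among primary successes? |
|---|---|
| Primary proportions and CI (4.2.1.4) | No |
| On-treatment supplement (4.2.1.6) | No; it carries a dose forward for more people, from IP discontinuation |
| Disposition (4.1.1.2) | Counts withdrawals, but not by primary outcome |
| OCS dose by visit (4.2.7.4) | Does not count successes |
| Participant-level listings (protocol 9.4.1) | Not as a summary |

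**4. Reproducing the plan's precision figure.** Inputs from SAP 1.3: N = 300, success rate 50%, two-sided 95% Clopper-Pearson interval. With x successes among n:

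- lower limit = 2.5% quantile of Beta(x, n − x + 1)
- upper limit = 97.5% quantile of Beta(x + 1, n − x)

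For x = 150 and n = 300 the limits are 44.2% and 55.8%, a half-width of 5.80 points. The stated 5.8 is confirmed.

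**5. Effect of recounting.** Suppose 150/300 is reported and c of those successes are carried forward from withdrawal. Counting them as non-responders gives (150 − c)/300, a shift of 100 × c/300 points, or 0.33 points each.

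| c | Shift (points) | Recounted | 95% CI |
|---|---|---|---|
| 0 | 0 | 50.0% | 44.2 to 55.8 |
| 3 | 1.0 | 49.0% | 43.2 to 54.8 |
| 6 | 2.0 | 48.0% | 42.2 to 53.8 |
| 15 | 5.0 | 45.0% | 39.3 to 50.8 |
| 17 | 5.67 | 44.3% | 38.6 to 50.2 |
| 18 | 6.0 | 44.0% | 38.3 to 49.8 |

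The shift first exceeds the distance to the lower limit at c = 18 for a 50% result (6.00 against 5.80). For 60% it is 18 (6.00 against 5.79), for 70% it is 17 (5.67 against 5.53), and for 80% it is 15 (5.00 against 4.98).

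**6. Range over an assumed withdrawal rate.** The documents give none, so 5% to 20% is my assumption. I also assume that half of those who withdraw were last stable as successes (rounded to whole people) and that about half of the completers succeed.

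| Withdrawn | Carried successes | Table 4 result | Counted as non-responders | Gap (points) |
|---|---|---|---|---|
| 15 (5%) | 8 | 150/300 = 50.0% | 142/300 = 47.3% | 2.7 |
| 30 (10%) | 15 | 150/300 = 50.0% | 135/300 = 45.0% | 5.0 |
| 45 (15%) | 22 | 150/300 = 50.0% | 128/300 = 42.7% | 7.3 |
| 60 (20%) | 30 | 150/300 = 50.0% | 120/300 = 40.0% | 10.0 |

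**The case against.** The rule is open and pre-specified. Table 4 stands directly before 4.2.1.3, matches the protocol, and falls under the exception in SAP 3.3. A reader might infer that the SAP contradicts itself about which analysis will be run. It does not: Table 4 governs, and what is missing is a cross-reference.

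A reader might also take the row "Any other situation" as a rule for missing doses. It is the default row and covers ordinary completers. The dose is a prescribed dose from the ECSYSCRT form, protocol 8.1.1 requires every dose change to be recorded, and reductions may be made remotely. Someone who misses a visit can still have a known dose, and calling that carry-forward would be wrong. Table 4 also does more than fill gaps: a dose recorded at the visit but changed less than two weeks before is replaced by the earlier stable one. Any rewording must fit that.

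A third inference is that withdrawals should count as failures because SAP 4.2.4.2 does so for the exacerbation-free proportion. That endpoint needs a whole period without events, which incomplete follow-up cannot establish. The primary endpoint is a dose status at a time point, so different rules are defensible. Nor do the documents support treating starters of another biologic as failures here: the sponsor chose a hypothetical strategy for them, and protocol Table 6 prohibits those drugs.

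On size, 18 carried successes at one success per two withdrawals means 18/0.5 = 36 of 300, or 12%, whereas protocol 7.2 expects withdrawal to be uncommon.

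All of this stands. What remains is that the carry-forward for withdrawals is a missing-data assumption that no planned output tests or counts.

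**Conclusion.** This is a cheap improvement, not an error in the primary analysis. The label in SAP 4.2.1.3 does not describe what Table 4 does for withdrawals, and the plan offers no way to see whether the reported proportions depend on it.

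The size is unknown. A handful of carried successes would move the result by one or two points, well inside the interval; 15 to 18, depending on the result, would be needed to move it by more than the distance to the lower limit. The figures rest on N = 300 and on the assumed rates in the last table of the working.

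A reader might infer that the reported proportion will be too high by the amounts shown. The documents do not support that. Counting withdrawals as non-responders gives a lower bound, not an estimate of bias, and Table 4 equally carries forward failures, such as a participant who leaves mid-taper above 5 mg.

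**What to change.** Keep Table 4 and the estimand as they are.

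1. Reword SAP 4.2.1.3, for example: *The final OCS dose is derived under Table 4, which uses the last dose stable for at least 2 weeks, including for participants who withdraw; no imputation is done beyond Table 4.*
2. In SAP 4.2.1.5, with the matching sentence of 4.2, add one sensitivity analysis of both primary endpoints at Weeks 28 and 52 on the FAS, with Clopper-Pearson intervals. Count as non-responders participants who withdrew from the study before the visit, or who have no ECSYSCRT prescribed-dose information covering the visit date (for example option 3 discontinuers whose dose is not recovered). A participant who misses the visit but has a recorded prescribed dose keeps the Table 4 status. Starters of another biologic keep the hypothetical strategy.
3. Report the number of primary successes by source of dose: covering the visit date; carried from withdrawal; carried from before another biologic; other, including a recorded dose replaced under the two-week rule.

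The cost is edits to three SAP sections and one extra table, from data already collected. The protocol needs no change. The downside is a companion figure that may look slightly less favourable. If few successes are carried, the same table shows that the result is robust.

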4.2.1.4 Primary Analysis of Primary Endpoint

Shit tables are provided showing the daily OCS dose at baseline versus the final OCS dose at Week 28 and the final OCS dose at Week 28 versus the final OCS dose at Week 52.

Each primary endpoint is summarised by number and proportion (with 95% CI) of participants. The 95% CIs for each proportion are calculated using the Clopper-Pearson exact method on the FAS and the currently or historically elevated EOS population.

4.2.1.5 Sensitivity Analyses of the Primary Endpoint

No sensitivity analysis.

^b Asthma stability is defined as no change in OCS dose for at least 2 consecutive weeks.

4.2.1.6 Supplementary Analyses of the Primary Endpoint

The number and proportion (with 95% CI), as described in Section 4.2.1.4, is repeated using on-treatment data only, where the definition of on-treatment is given in Section 3.3.1.1. The final daily OCS dose for a participant withdrawing from the study or prematurely discontinuing IP (regardless of chosen option) is the last reported OCS dose received by the participant when asthma stability was verified, at the time of IP discontinuation, as described in Table 4 in Section 4.2.1.2. The derivation of the final daily OCS dose for any other participant is following the rules described in Table 4.

The analysis is performed based on both FAS and the currently or historically elevated EOS population.

4.2.1.7 Subgroup Analyses

The number and proportion with 95CI%, as described in Section 4.2.1.4, is also presented by the following pre-specified subgroups for both primary (Week 28) and final (Week 52) analysis:

- Eosinophils (EOS) at baseline group: $< 300/\mu L, \ge 300/\mu L$
- Eosinophils (EOS) at baseline group: $< 150/\mu L, \ge 150/\mu L$
- Eosinophils (EOS) at baseline group: <150, >=150 to <300, >=300
- Eosinophils (EOS) at screening group: <150 with documented high EOS, $<150/\mu$ L without documented high EOS, $>=150/\mu$ L
- Baseline FeNO group: $< 25 \text{ ppb}, \ge 25 \text{ ppb}$
- Baseline (Any) specific IgE status (FEIA): Any FEIA positive, All FEIA negative, Unknown FEIA (see Section 4.1.5.1)
- Baseline perennial specific IgE status (FEIA): Any perennial FEIA positive, All perennial FEIA negative, Unknown perennial FEIA (see Section 4.1.5.1)
- Baseline seasonal specific IgE status (FEIA): Any seasonal FEIA positive, All seasonal FEIA negative, Unknown seasonal FEIA (see Section 4.1.5.1)
- Eosinophils (EOS) at baseline and baseline perennial specific IgE status (FEIA):
 - \circ EOS < 150/ μ L and with any perennial FEIA positive
 - EOS $\geq 150/\mu$ L to $< 300/\mu$ L and with any perennial FEIA positive
 - EOS $\ge 300/\mu$ L and with any perennial FEIA positive
 - O EOS < 150/μL and with all perennial FEIA negative
 - o EOS ≥ $150/\mu$ L to < $300/\mu$ L and with all perennial FEIA negative
 - EOS $\ge 300/\mu$ L and with all perennial FEIA negative
- Daily OCS dose at baseline: (≤10 mg versus >10 mg prednisone or prednisolone)
- Regions: Central/Eastern Europe (low availability of biologics), Western Europe (high availability of biologics), South America, North America (see Section 4.1.1.1)

- Therapy reason for SCS use related to AI: Yes (includes the following therapy reasons: AI based on cortisol test, Signs/symptoms of AI, Adrenal Crisis), No (all remaining therapy reasons)
- Access to ACTH Test (ACTH is not available in Poland, Bulgaria and Latvia, ACTH available in all the remaining countries)

For the final (Week 52) analysis additionally the following subgroups will be presented:

- Adrenal Insufficiency status measured when a participant reaches 5mg of daily OCS dose: Normal, Partial AI, Complete AI.
- Countries: for the list of countries see Section 4.1.1.1

Subgroup analyses are performed on the FAS. If any of the subgroups have fewer than 10 participants in a level, then this subgroup level is not included in any model. If that leaves only one subgroup level, the analysis is not performed for that categorical variable.

4.2.1.8 Interim Analysis of Primary Endpoint

The derivation of the final daily maintenance OCS dose as described in Section 4.2.1.2 cannot be applied due to the reason mentioned in Section 4.2. Alternatively, for each post-baseline visit the latest daily maintenance OCS dose at the time of the visit is used as described in Section 4.2.7.2.

The number and proportion of participants who discontinued OCS or reduced OCS dose to ≤ 5 mg/day is summarised over time on the FAS.

4.2.2 Secondary Endpoint - Annual asthma exacerbation rate (AAER) over Week 28 and Week 52

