4.2.5.7 Interim Analysis of Secondary Endpoint

The derivation of baseline, post-baseline and change from baseline in daily maintenance OCS dose is described in Section 4.2.7.2.

The number and proportion of participants with $\geq 50\%$ reduction from baseline in daily maintenance OCS dose is summarised over time on the FAS.

4.2.6 Secondary Endpoint - Categorised percent reduction from baseline in the daily maintenance OCS dose at Week 28 and Week 52.

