4.2.15.7 Interim Analysis of Exploratory Endpoint

The derivation of ACQ-6 responder is presented in Section 4.2.15.2.

The number and proportions of ACQ-6 responders, non-responders and missing data are presented over time on the FAS.

4.2.16 Exploratory Endpoint - Proportion of AQLQ(s)+12 responders at Week 28 and Week 52

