4.2.19.4 Primary Analysis of Exploratory Endpoint

The absolute values and absolute changes from baseline in SNOT-22 score are summarised using descriptive statistics over time. The number and proportions of SNOT-22 responders, non-responders and missing data are also presented over time. All data available at primary DBL is presented, which includes data beyond Week 28 (see Section 3.1).

The analyses are performed based on the FAS.

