5 INTERIM ANALYSIS

An interim analysis may be performed if approximately 50 participants complete V4 before a data cut-off date planned on mid-April 2023. All data available for participants who completed Visit 4 prior to the data cut-off date will be included. The results are not used to change any element of the study design and the study continues regardless of the results of interim analysis.

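### The interim by-visit OCS proportions keep participants not yet due for a visit in the denominator, so from Week 12 onward they are understated

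*SAP*

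**What the plan says.** - **Default denominator (SAP 3.3):** "For participants' proportion calculation, the denominator is the number of participants in the Full Analysis Set defined in Section 4.1.2 unless otherwise stated".
- **Interim primary endpoint (SAP 4.2.1.8):** the number and proportion of participants "who discontinued OCS or reduced OCS dose to ≤ 5 mg/day is summarised over time on the FAS". The final-dose rule of SAP 4.2.1.2 is set aside; instead, "for each post-baseline visit the latest daily maintenance OCS dose at the time of the visit is used as described in Section 4.2.7.2". No denominator by visit, number due or missing category is given.
- **Interim secondary endpoint (SAP 4.2.5.7):** the share with at least a 50% "reduction from baseline in daily maintenance OCS dose is summarised over time on the FAS", again with no other denominator.
- **Who is included (SAP 5):** "All data available for participants who completed Visit 4 prior to the data cut-off date will be included". The trigger is about 50 such participants by mid-April 2023.
- **By-visit dose (SAP 3.3.2):** the OCS window for a visit is built from the actual date of that visit. A participant with no value in a window is missing there. SAP 4.2.1.3 and 4.2.5.3 allow no imputation.
- **Purpose (Protocol 9.5):** the interim is meant for publication and does not alter the design.

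**The concern.** The cut-off is a calendar date, so the included participants have different lengths of follow-up, starting at about 8 weeks. Someone whose Week 16 visit lies after the cut-off has no Week 16 dose. Under the default rule that person still counts in the Week 16 denominator and cannot count in the numerator. This is administrative non-observation, yet the table shows it as failure to reduce OCS.

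The affected visits are the informative ones for discontinuation. On the schedule in Protocol Table 7 and 8.2.1, a participant starting above 5 mg/day reaches 5 mg at Week 4 at the earliest. The cortisol test follows four weeks later, at Week 8. With a normal result the dose is then 2.5 mg from Week 8 and zero from Week 12. Only participants who start at exactly 5 mg could be at zero by about Week 8. Nearly all of the interim evidence on stopping OCS therefore sits at visits where the denominator is inflated, in a table intended for publication.

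**Working it through.** **1. The plan's own figures.** SAP 1.3 gives Clopper-Pearson 95% distances at 50% success of ±14.5 points for n = 50 and ±5.8 for n = 300. Recomputed from beta quantiles, 25/50 gives ±14.47 and 150/300 gives ±5.80, so these reproduce. The plan states no by-visit interim figure to check.

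**2. A bound that needs no accrual assumption.** Let N be the interim set, R(w) the number with a Week w visit by the cut-off, and S(w) the successes among them.

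Printed proportion = S(w)/N = [R(w)/N] × [S(w)/R(w)] ≤ R(w)/N.

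The printed value is the success proportion among those observed, shrunk by the fraction observed. All Visit 4 completers have reached Weeks 4 and 8, so the shrinkage starts at Week 12.

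**3. Illustration.** Assumptions, not in the documents: N = 50, follow-up spread evenly from 8 to 28 weeks, true success constant at 50%. The upper end is chosen because SAP 4.2 says that these participants' duration is shorter than the Week 28 evaluation. Then R(w) = 50 × (28 − w)/20.

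| Week | Reached R | Successes S | Printed S/50 | S/R |
|---|---|---|---|---|
| 8 | 50 | 25 | 50% | 50% |
| 12 | 40 | 20 | 40% | 50% |
| 16 | 30 | 15 | 30% | 50% |
| 20 | 20 | 10 | 20% | 50% |
| 24 | 10 | 5 | 10% | 50% |

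If an exact interval is attached under the general rule in SAP 3.3, Week 24 as 5/10 has limits 18.7% to 81.3%. Printed as 5/50 it reads 3.3% to 21.8%, which is both too low and too narrow.

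**4. Range over the longest follow-up.** Same assumptions otherwise, counts rounded to whole participants:

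- 20 weeks: 16/50 = 32% at Week 12, 8/50 = 16% at Week 16, and nobody observed by Week 24.
- 40 or 52 weeks (outside what SAP 4.2 describes): 38% or 40% at Week 16, and 24% or 32% at Week 24.

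**5. Rising true curves.** Stepwise titration makes a constant success proportion unrealistic, so two assumed curves were tried for Weeks 8/12/16/20/24, with N = 50:

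- 5 mg/day or less, true 35/55/65/70/70%, follow-up to 28 weeks: prints 36/44/40/28/14%.
- Zero dose, true 5/12/22/32/40%, follow-up to 28 weeks: prints 4/10/14/12/8%.
- Zero dose, same curve and 45% at Week 28, follow-up to 52 weeks: prints 4/10/18/24/26%, then 24% at Week 28.

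Every case is understated from Week 12. Whether the printed series visibly falls depends on accrual and on the true curve.

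**The case against.** **Timing.** The planned cut-off, mid-April 2023, is about seven months before SAP edition 5.0 (9 November 2023), and the interim was optional. A sentence added now cannot govern that analysis prospectively. This limits the practical effect, but edition 5.0 still carries the rule as current text, and any published table can be checked.

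**Low stakes.** The interim is descriptive, tests no hypothesis and changes nothing in the design. That is true. Its stated use is publication, though, and this is its primary-endpoint table.

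**A carry-forward reading.** SAP 4.2.7.2 refers back to 4.2.1.2 for the by-visit dose. Using the last stable dose could fill the later visits and remove the dilution. But 4.2.1.8 says that the 4.2.1.2 derivation cannot be applied at the interim. The circular reference is a further reason to state the rule.

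**Stronger readings that a reader might infer, which the documents do not support:**

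- *Published success would fall week by week.* Understatement follows from the rule; a fall does not (step 5), and the documents give no accrual curve or count per visit.
- *All dosed participants form the denominator, so Week 8 is diluted too.* With 60, 75 or 100 dosed and 50 at Week 8, a true 50% would read 42%, 33% or 25%. SAP 5, however, limits the interim data to Visit 4 completers.
- *The Week 28 and Week 52 primary results are diluted.* They use the final dose in SAP Table 4, not by-visit values.
- *The ACQ-6 and SNOT-22 responder tables hide the same problem.* They divide by the FAS (SAP 4.2.15.2, 4.2.19.2), but for ACQ-6, "The number and proportions of ACQ-6 responders, non-responders and missing data are presented over time on the FAS", and SAP 4.2.19.4 likewise prints a missing category for SNOT-22. A reader can see the effect and re-base the figures.

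**Conclusion.** The point stands for the interim OCS proportions in SAP 4.2.1.8 and 4.2.5.7. Read with SAP 3.3, they count a participant whose visit lies after the cut-off as a non-success. At any visit from Week 12 onward that some included participants have not reached, the printed proportion is understated and is capped at the fraction observed. It may fall at the latest visits, but a fall is not certain. Weeks 4 and 8 are unaffected.

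The size depends on accrual, which the documents do not give. In the step 3 illustration the shortfall from a true 50% grows from 10 points at Week 12 to 40 points at Week 24. The direction and the cap need no such assumption. This is a wrong rule for the data it is applied to, not merely a missing detail, but its reach is confined to the interim tables. The same denominator question touches SNOT-22 responders at the primary lock, where "All data available at primary DBL is presented, which includes data beyond Week 28", though there the missing category already exposes it.

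**What to change.** In SAP 4.2.1.8 and 4.2.5.7, state that the denominator at each visit is the interim FAS participants (Visit 4 completers) whose scheduled visit, including its +5-day window, falls on or before the data cut-off. In dates: first dose + 7 × week + 5 days ≤ cut-off, for example first dose + 89 days for Week 12. Count successes among the same participants. Keep in those who withdrew or missed a visit that was due. Print n/N and a missing count at each visit. The rule should rest on scheduled date plus window, because SAP 3.3.2 excludes the Table 3 windows for OCS dose and a bare target day would leave in people who may still attend within the window.

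Apply the same denominator to ACQ-6 responders at the interim (SAP 4.2.15.7) and to SNOT-22 responders beyond Week 28 at the primary lock (SAP 4.2.19.2 and 4.2.19.4).

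If the interim has already been run, check the denominators used and re-base any published proportions if needed.

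Cost: one sentence repeated in the sections named and no new data; at most, a rerun of the affected tables.
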